9.2.2. OCSTM Heart Population

The OCSTM heart population will consist of all donor hearts that are transported by the OCSTM. The analysis of the rate of donor hearts utilization that were successfully transplanted after preservation and assessment on the OCSTM heart device will be based on the OCSTM heart population.

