Primary heart transplant candidates will be screened for trial eligibility. Every eligible candidate will be asked to participate. Eligible heart transplant candidates will receive OCS TM preserved donor hearts that have been deemed clinically acceptable for transplantation by the treating transplant clinical team.
Inclusion
At least one of the following:
 Expected total cross-clamp time of ≥ 4 hours Expected total cross-clamp time of ≥ 2 hours PLUS one of the following risk factors: Donor age 45-55 years old with no coronary catheterization data, or Donor age ≥ 55 years old; or Left ventricular septal or posterior wall thickness of >12 ≤16 mm; or Reported down time of ≥ 20 min, with stable hemodynamics at time of final assessment; or Left heart ejection fraction (EF) ≥ 40 ≤ 50%; or Donor angiogram with luminal irregularities with no significant CAD History of Carbon monoxide poisoning with good cardiac function at time of donor assessment Social history of alcoholism with good cardiac function at time of donor assessment; or History of diabetes combined with negative coronary angiogram for coronary artery disease (CAD).

Page 5 of 44

	Exclusion
	• Angiogram proven CAD with >50% stenosis, or
	Cardiogenic shock or myocardial infarction, or
	• Sustained terminal EF of <40%, or
	Significant valve disease except for competent bicuspid aortic valve.
Recipient	Inclusion
Eligibility	Registered male or female primary Heart transplant candidate
Criteria	• Age \geq 18 years old
	• Signed: 1) written informed consent document and 2) authorization to use and disclose protected health information.
	Exclusion
	Prior solid organ or bone marrow transplant
	Chronic use of hemodialysis or diagnosis of chronic renal insufficiency
	Multi-organ transplant.
Donor Heart	Accept for Transplantation
on OCS TM	Donor hearts preserved on the OCS TM should be maintained within the following parameters:
Transplant	Total OCS TM arterial Lactate level < 5 mmol/L
Criteria	Stability of OCS TM Heart Perfusion Parameters within ranges:
0110011	• CF 400-900 ml/min
	o AOP 40-100 mmHg
	0 1101 40-100 mining
	Reject for Transplantation
	Total OCS TM arterial Lactate Level >5 mmol/L at the end of OCS TM perfusion period
	• •
	Transplanting surgeon/heart failure cardiologist clinically unsatisfied with donor heart OCSTM (15) OCSTM (
D :	evaluation on OCS TM (If yes, specify reason).
Primary	A composite endpoint of patient survival at Day-30 post-transplant and absence of severe primary heart

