Endpoint	graft dysfunction (PGD) (left or right ventricle) in the first 24 hours post-transplantation.
Secondary	Patient survival at day-30 post-transplantation.
Endpoints	• Incidence of severe primary heart graft dysfunction (PGD) (left or right ventricle) in the first 24
	hours post-transplantation.
	Rate of donor hearts utilization that were successfully transplanted after preservation and
	assessment on the OCS™ heart device.
Safety	Incidence of heart graft-related Serious Adverse Events (SAEs) in the first 30 days post heart
Endpoint	transplantation, defined as:
_	 Moderate or Severe primary heart graft dysfunction (PGD) (left or right ventricle) (not
	including rejection or cardiac tamponade). Please see Appendix 2 for detailed definition of LV
	and RV PGD according to ISHLT consensus manuscript. Primary graft failure requiring re-
	transplantation.
Follow-up	All patients will be followed for up to 1 year post-transplant.
Statistical	Analysis Populations
Methods	The transplanted recipient population will consist of all recipients who are transplanted according to
	this protocol and who have no major protocol violations. The analyses of all effectiveness and safety
	endpoints, except the rate of donor hearts utilization that were successfully transplanted after
	preservation and assessments on the OCS TM heart device, will be based on the transplanted recipient
	population.
	r · r · · · · · · · · · · · · · · · · ·
	The OCS TM heart population will consist of all donor hearts that are transported by the OCS TM . The analysis of the rate of donor hearts utilization that were successfully transplanted after preservation and
	assessment on the OCS TM heart device will be based on the OCS TM heart population.

Effectiveness

The primary hypothesis for this trial is that the true proportion of transplanted recipients with composite patient survival at Day 30 post-transplantation and absence of severe primary heart graft dysfunction (PGD) (left or right ventricle) in the first 24 hours post-transplantation is greater than the Performance Goal value of 0.65. The primary statistical hypotheses are as follows:

 H_0 : $\pi \le 0.65$ and H_1 : $\pi > 0.65$,

where π is the true proportion of transplanted recipients with patient survival at Day 30 and absence of severe primary heart graft dysfunction (PGD) (left or right ventricle) in the first 24 hours post-transplantation

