6.4. Donor Heart Retrieval and OCSTM Preservation and Assessment

After final evaluation of the donor heart in donor's chest and upon acceptance into the trial, the investigators will retrieve and preserve the donor heart according to the following protocol:

• Initial Heart Flush in Donor Body: all donor hearts will be arrested using 750-1000 ml of cold Del Nido heart arrest and flush solution OR identical chemical formulation (see below) flush via the aortic root according to standard retrieval procedure.

Del Nido Solution Formulation	Concentration
Base Solution 1 Liter	Components (mmol/L)
Na	140
Cl	98
K	5
Mg	3
Acetate	27
Gluconate	23
рН	7.4 (6.5-8)
Additives	(ml/L base solution)
KCL 2mEq/L	13
NaHCO3 1mEq/ml	13
MgSO4 50% - 0.5 g/ml	4
Lidocaine 1%	13
Mannitol 20%	16

- OCSTM Heart Perfusion: The OCSTM Heart system will be primed using:
 - 1.2-1.5 L of donor blood
 - 100-300 ml of 25% albumin solution
 - 300-500 ml of OCS™ Heart priming solution
 - Hearts preserved on the OCSTM Heart should be maintained according to the OCSTM Heart Instructions for use (IFU).

- Lactate Level and other chemistries sampling scheme: The organ retrieval team will collect samples from the donor and from the arterial and venous ports of the device and measure lactate levels using a standard blood gas analyzer according to the following protocol:
 - One blood sample will be collected from the donor prior to cross clamp (Donor Baseline Sample)
 - One blood sample will be collected after the donor's blood is added to the OCS™ circuit and prior to instrumentation of the donor's heart (Pre-instrumentation Sample).
 - One arterial and one venous sample will be collected within 10-20 minutes of perfusing the heart on the OCSTM Heart device.
 - At least, one additional arterial and venous sample will be collected before leaving the donor site.
 - Samples will continue to be collected from the device at approximately hourly intervals and after any active CF adjustment or any other adjustments.
- The OCSTM Heart Preservation Parameters: The OCSTM device parameters should be maintained within the following ranges after stabilization of the organ
 - Aortic Pressure (mean AOP): 40-100 mmHg
 - Coronary Flow (CF): 400-900 ml/min
 - Perfusate Temperature (Temp): 34°C
 - Circulating total Lactate (Lact): < 5 mmol/L

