6.5. Donor Heart Acceptance for Transplantation

- To maximize safety to potential recipients, the surgical procedure should not be initiated on the recipient until the donor heart has been clinically accepted by the transplanting surgeon/physician based on the below acceptance criteria.
- All donor hearts preserved on OCSTM Heart must meet the following clinical criteria for transplantation at final assessment on OCSTM Heart (Final Sample):

- Final total arterial circulating OCSTM Heart perfusate Lact. Level < 5 mmol/L with stable lactate trend.
- Stable CF, AOP trends within above ranges (certain expanded criteria organs, i.e., LVH hearts, may require higher CF and/or AOP to achieve adequate perfusion).
- Any decision to turn down hearts after the hearts have been retrieved, preserved and assessed on OCSTM Heart should be done with notification to the Site PI and the donor heart must be examined by the transplant center's qualified cardiac transplant pathologist and a central core lab for further assessment to evaluate any inherent cardiac pathology that was not diagnosed at retrieval of the donor heart.

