6.0 ANALYSIS POPULATIONS

The Transplanted Recipient Population will consist of all recipients who are transplanted according to the OCS™ Heart protocol and who have no major protocol violations. The analyses of all effectiveness and safety endpoints, except the rate of donor hearts utilization that were successfully transplanted after preservation and assessment on the OCS™ heart device, will be based on the Transplanted Recipient Population.

For this study, major protocol violations include:

- Donor and recipient's Inclusion/Exclusion Criteria Violation
- Failure to follow IFU
- Failure to follow protocol

The OCS™ Heart Population will consist of all donor hearts that are transported by the OCS™. The analysis of the rate of donor hearts utilization that were successfully transplanted after preservation and assessment on the OCS™ heart device will be based on the OCS™ Heart Population.

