12.2 Secondary Effectiveness Analyses

The secondary effectiveness endpoints are as follows:

1. Patient survival at Day 30 post-transplantation
2. Incidence of severe primary graft dysfunction (PGD) (left or right ventricle) in the first 24 hours post-transplantation
3. Rate of donor hearts utilization that were successfully transplanted after preservation and assessment on the OCS™ heart device

These endpoints will be summarized using frequencies and percentages and exact (Clopper-Pearson) 95% confidence intervals for the true population percentages. The first two secondary effectiveness endpoints will be analyzed based on the Transplanted Recipient Population (Table 4.1). The third endpoint, which is the ratio of the number of successfully transplanted donor hearts divided by the number of donor hearts in the OCS™ Heart Population, will be analyzed based on the OCS™ Heart Population (Table 4.1).

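### The OCS Heart Population counts hearts transported by the device; taken literally, a trial heart lost on the device before leaving the donor site drops out of the utilization rate

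*Protocol*

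**What the plan says.** The population is defined three times, each time by transport. Protocol section 9.2.2: "The OCSTM heart population will consist of all donor hearts that are transported by the OCSTM". The protocol synopsis, under Analysis Populations: "The OCS TM heart population will consist of all donor hearts that are transported by the OCS TM". SAP section 6.0: "The OCS™ Heart Population will consist of all donor hearts that are transported by the OCS™". Neither document defines the word or names the event that brings a heart into the population.

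SAP section 12.2 defines the third secondary endpoint, utilization, as "the ratio of the number of successfully transplanted donor hearts divided by the number of donor hearts in the OCS™ Heart Population", with an exact 95% confidence interval and no test or goal. The same population is the base for Table 1.2 (donor heart disposition, SAP section 7.0), Table 3.4 (device malfunction, SAP section 10.0), and Supplemental Tables 2.4.1, 2.5 to 2.9 and 3.1 to 3.3.

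Protocol section 6.4 gives the order of events. Trial entry comes before retrieval: "upon acceptance into the trial, the investigators will retrieve and preserve the donor heart according to the following protocol". The heart is then instrumented and perfused, with arterial and venous samples 10 to 20 minutes into perfusion. After that, "At least, one additional arterial and venous sample will be collected before leaving the donor site".

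**The concern.** There is a stretch of time in which a heart is in the trial and on the investigational device but has not been transported. In that time it is exposed to device malfunction, to poor perfusion and to a clinical decision against using it. If it is lost or turned down then, the wording leaves it out of the utilization denominator and out of the summary tables that should account for it. Such a heart cannot be in the numerator, so leaving it out can raise the rate but cannot lower it. With a single arm, there is no comparator in which the effect could cancel.

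The synopsis objective speaks of improving donor heart utilization, and this is the listed endpoint closest to that aim. A malfunction at the donor site would also be missing from Table 3.4, where a reader would look for it.

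**Working it through.** **Text check.** The relevant wording, side by side:

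- Definition (synopsis, Protocol 9.2.2, SAP 6.0): hearts transported by the OCS.
- Workflow (Protocol 6.4): accepted into the trial, retrieved, instrumented, perfused, sampled at least twice on the device, and only then away from the donor site.
- Endpoint (Protocol 4.2, SAP 4.2): hearts successfully transplanted following OCS preservation and assessment. Transport is not mentioned.
- Disposition (SAP 7.0, Table 1.1): recipients matched to a heart that was turned down after OCS. Transport is not mentioned.

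So a heart could be counted as a turn-down in Table 1.1, which counts recipients, and be absent from Table 1.2, which counts hearts. *Transported* does not mean a completed preservation run either, because a heart that fails in transit has been transported.

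**Arithmetic.** The documents give no expected or target utilization rate, so there is no plan figure to reproduce. The following is an illustration.

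Inputs:
- T = 75 transplanted: the maximum in Protocol 3.2 and SAP 3.1.
- N = hearts transported: not given; assumed 80, 90 or 100.
- k = hearts instrumented, then lost or turned down before leaving the donor site: not given; assumed 1 to 5, and 0 is possible.

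Rate as defined: T/N. Rate over all instrumented hearts: T/(N + k). Overstatement: T/N − T/(N + k) = (T/N) × k/(N + k).

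| N | T/N | k = 1 | overstated by | k = 5 | overstated by |
|---|---|---|---|---|---|
| 80 | 93.8% | 75/81 = 92.6% | 1.2 points | 75/85 = 88.2% | 5.5 points |
| 90 | 83.3% | 75/91 = 82.4% | 0.9 points | 75/95 = 78.9% | 4.4 points |
| 100 | 75.0% | 75/101 = 74.3% | 0.7 points | 75/105 = 71.4% | 3.6 points |

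Exact (Clopper-Pearson) 95% intervals at N = 90: 75/90 gives 74.0 to 90.4%, 75/91 gives 73.0 to 89.6%, and 75/95 gives 69.4 to 86.6%.

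**Scale against sampling error.** This is the smallest k at which T/(N + k) falls below the lower limit reported for T/N:

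- N = 80, lower limit 86.01%: k = 8 (75/88 = 85.23%; k = 7 gives 86.21%).
- N = 90, lower limit 74.00%: k = 12 (75/102 = 73.53%; k = 11 gives 74.26%).
- N = 100, lower limit 65.34%: k = 15 (75/115 = 65.22%; k = 14 gives 65.79%).

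A few omitted hearts would move the estimate but leave it well inside the reported interval.

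**The case against.** The strongest reply is that the drafters meant every heart placed on the OCS. The endpoint is worded around preservation and assessment on the device. SAP section 10.0 also uses this population for malfunctions and for chemistry from pre-instrumentation onwards, which suits an on-device population better than one that starts at departure. This may well be the intent. If so, only the wording needs repair, but three identical definitions still say something narrower.

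A second reply is that the documents describe no rejection step at the donor site. Protocol section 6.5 ties the acceptance criteria to the final sample, and the synopsis places lactate rejection late: "Total OCS TM arterial Lactate Level >5 mmol/L at the end of OCS TM perfusion period". The sample before departure has no decision rule attached. This stands as a limit on the point. It does not close the gap, because the synopsis also lists rejection on clinical judgement without a time, and a device can fail at any time.

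Third, the hearts are not lost from the record. Listings 19, 20, 22 and 23 cover disposition, instrumentation, acceptance and malfunction. That is true, but a listing does not correct a denominator. The table shells and case report forms are not visible and might fix the entry event.

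Fourth, *instrumented* also needs an anchor, and a heart lost after retrieval but before instrumentation would still be outside. That is fair. Instrumentation is at least an event for which the SAP already has a listing.

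Three stronger readings are tempting, and the documents do not support them:

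- A reader might infer that the utilization rate is in fact biased. Nothing shows that any heart is lost in this interval; if none is, there is no bias.
- A reader might infer that every heart the wording excludes is a failure. That holds for hearts lost or turned down. A heart perfused on the OCS with donor and recipient in the same hospital would, read literally, not be transported either, yet could be transplanted.
- A reader might infer that the trial's main conclusion is at risk. The primary endpoint is analyzed in the Transplanted Recipient Population and is untouched.

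**Conclusion.** The point holds as a conditional one. As written, the definition excludes a trial heart that was on the device but lost or turned down before departure, and for such hearts the exclusion can only flatter the utilization rate. The documents do not show that this happens. With T = 75 and N assumed between 80 and 100, each omitted heart adds about 0.7 to 1.2 points and five add 3.6 to 5.5 points; N and k are assumptions. The endpoint is descriptive, and the primary test, its alpha and the sample size do not change. This is a cheap improvement worth making before the rate is computed, not a flaw in the trial's main inference.

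**What to change.** In the synopsis, Protocol section 9.2.2 and SAP section 6.0, define the OCS Heart Population as all donor hearts accepted into the trial and instrumented on the OCS, whether or not transported, and name the instrumentation record behind Listing 20 as the entry event. Use this population for the utilization rate (numerator unchanged), Tables 1.2 and 3.4, and the supplemental OCS Heart Population tables. Add a row to Table 1.2 for hearts lost or rejected before leaving the donor site. In Supplemental Tables 3.1 to 3.3, give the number of hearts with data, since such a heart may have no final sample.

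The cost is one sentence in three places and one table row. Device malfunction and non-transplant reasons are already scheduled under OCS Preservation in Protocol Appendix 3, so new data should not be needed, though the case report forms are not visible to confirm this. The downside for the sponsor is a possibly slightly lower reported rate.

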9.3. Analysis of Effectiveness Endpoints

9.3.1. Primary Effectiveness Endpoint

The primary hypothesis for this trial is that the true proportion of transplanted recipients with the composite of patient survival at Day 30 post-transplantation and absence of severe primary heart graft dysfunction (PGD) (left or right ventricle) in the first 24 hours post-transplantation is greater than the Performance Goal value of 0.65. The primary statistical hypotheses are as follows:

 H_0 : $\pi \le 0.65$ and H_1 : $\pi > 0.65$

where π is the true proportion of transplanted recipients with patient survival at Day 30 and absence of severe primary heart graft dysfunction (PGD) (left or right ventricle) in the first 24 hours post-transplant.

The primary effectiveness endpoint will be summarized using counts and percentages and an exact 95% confidence interval for the true percentage based on the binomial distribution. A one-sided exact binomial test at the 0.05 significance level will be performed to test the null hypothesis H₀. This endpoint will be analyzed using the transplanted recipient population.

9.3.2. Secondary Endpoints

The secondary endpoints for this trial are as follows:

- Patient survival at day-30 post-transplantation
- Incidence of severe primary heart graft dysfunction (left or right ventricle) in the first 24 hours post-transplantation
- Rate of donor hearts utilization that were successfully transplanted after preservation and assessment on the OCSTM heart device.

Each secondary effectiveness endpoint will be summarized using counts and percentages and an exact 95% confidence interval for the true percentage based on the binomial distribution. The first two secondary effectiveness endpoints will be analyzed using the transplanted recipient population. The rate of donor hearts utilization that were successfully transplanted after preservation and assessment on the OCSTM heart device, will be analyzed using the OCSTM heart population.

9.4. Analysis of Safety

Safety will be analyzed principally by examination of the frequency of adverse events. In particular, the number of donor heart graft-related serious adverse events (SAEs) up to the 30-day follow-up after transplantation per subject will be analyzed. This endpoint is defined to consist of the following adverse events (at most one per type), if they are serious adverse events:

- Primary heart graft dysfunction (not including rejection or cardiac tamponade):
 - Use of ECMO, RVAD, LVAD, BiVAD or insertion of a new IABP for >12 hours post TX.
 - Use of ≥ 2 inotropic agents/vasopressors including high-dose epinephrine or norepinephrine for >7 days post heart TX.
 - Open chest post heart TX. due to compromised heart function
- Primary graft failure requiring re-transplantation

This endpoint will be summarized using descriptive statistics. A 95% confidence interval for the mean based on the t-distribution will be presented.

This endpoint will be analyzed based on the transplanted recipient population.

In addition, the numbers and percentages of subjects experiencing at least one heart graft-related AE, at least one (definitely or probably-related) device-related AE, at least one unanticipated AE, and at least one serious AE, and the number and percentage of deaths will all be tabulated. Also, the number of heart graft-related adverse events and the number and percentage of subjects experiencing adverse events will be tabulated by system organ class and preferred term using MedDRA. A similar analysis will be performed for serious AEs. AEs will also be tabulated at the event level by system organ class and preferred term and the relationship of the adverse event to the device using counts and percentages. Similar analyses will be performed by the severity of the adverse event.

9.5. Site Poolability

A site effect analysis will be conducted to assess the poolability of data. Sites with fewer than five subjects will be grouped into a larger Analysis Site. A chi-square test will be performed to evaluate site impact with a p-value of 0.15 defined as the threshold. If the p-value < 0.15 then analysis adjusting for site will be considered.

9.6. Sample Size Determination

The sample size for this trial was determined based on the primary effectiveness composite endpoint of patient survival at Day 30 post-transplantation and absence of severe primary heart graft dysfunction (PGD) (left or right ventricle) in the first 24 hours post-transplantation. The calculation assumed a one-sided exact binomial test, an alpha level of 0.05, a Performance Goal of 0.65, a true survival rate for OCSTM of 0.80, and power of 80%. Based on these specifications, the required sample size was determined to be 55 transplanted recipients. Assuming that there are exactly 55 transplanted recipients in the study, the null hypothesis will be rejected only if at least 76.4% (i.e., 42 of the 55 recipients) meet the primary endpoint.

